3.2 Primary and Secondary Endpoints and Evaluations

3.2.1 Primary Efficacy Endpoint and Evaluation

The primary efficacy endpoint is as follows:

• the percentage of responder subjects at Week 6 after the second injection, according to composite AROM in the primary TT limb.

Composite AROM (X_A), regardless of whether the muscle groups were injected or not, as measured by goniometer in the primary TT limb (either UL or LL, depending on which one has been selected as the primary TT limb), will be calculated as follows:

- composite X_A UL: X_A UL = X_{AEF} + X_{AWF} + X_{AFF}
- composite $X_A LL$: $X_A LL = X_{Asol} + X_{AGN}$

where for UL: EF=elbow flexors, WF=wrist flexors and FF=extrinsic finger flexors, and for LL: Sol=soleus and GN=gastrocnemius muscles.

Definition of a responder: a subject will be considered a responder if he/she achieves at least the predefined improvement threshold - larger or equal to 35° in UL or 5° in LL - in the primary TT limb (based on the composite AROM individual change from baseline to Week 6 after the second injection).

3.2.2 Secondary Efficacy Endpoints and Evaluations

The secondary efficacy endpoints are as follows:

- the percentage of responder subjects at Week 6 after the first injection, according to composite AROM in the primary TT limb
- AROM against 10 prespecified muscle groups, 5 in upper and 5 in lower limbs: mean change from baseline at Week 6, Week 12 and re-injection/last cycle visits only
- composite AROM against injected muscle groups (any of the 10 prespecified), in upper and lower limbs: mean change from baseline at Week 6, Week 12 and re-injection/last cycle visits only
- full composite AROM against five UL muscle groups (X_A full UL = $X_{ASE} + X_{AEF} + X_{AWF} + X_{AFF} + X_{AFF} + X_{AFF} + X_{AFF} + X_{AFF} + X_{AFF} + X_{AFF}$) or full composite AROM against five LL muscle groups (X_A full LL = $X_{Asol} + X_{AGN} + X_{AGM} + X_{AHS} + X_{ARF}$), regardless of whether the muscle groups were injected or not: mean change from baseline at Week 6, Week 12 and re-injection/last cycle visits only

where for UL: SE=shoulder extensors, EF=elbow flexors, WF=wrist flexors, FF=extrinsic finger flexors and PT=pronator teres,

and for LL: Sol=soleus, GN=gastrocnemius muscles, GM=gluteus maximus, HS=hamstrings and RF=rectus femoris

- active UL function measured using MFS: mean change from baseline in MFS overall score (i.e. mean score over the 10 tasks assessed locally and centrally by a reviewer blinded regarding the date of the video recording/visit number) at Week 12 after each injection cycle
- active LL function measured using maximal WS barefoot without walking aids or, if absolutely necessary, with a cane, measured on a 10-metre WST: mean change from baseline at Week 12 after each injection cycle. (If a cane is used at the Baseline Visit, the same cane is to be used during all WS assessments.)
- subject satisfaction with the GSC: at baseline (only for patients who had GSC performed previously), Week 6, Week 12 and re-injection/last cycle visits only

PROTOCOL FINAL (INCLUDING AMENDMENT #2): 24 JANUARY 2018

- changes in subject's beliefs that the GSC will help to improve functional capacity: change from baseline to Week 6, Week 12 and re-injection/last cycle visits only
- changes in Physiotherapist's belief that the GSC will help to improve functional capacity: change from baseline to Week 6, Week 12 and re-injection/last cycle visits only
- subject compliance with the GSC: percentage of days over study period when GSC therapy was performed (as determined from the subject diary)
- global assessment of benefits, evaluated by both the investigator and the subject (or caregiver): at the end of each cycle
- in subjects with an injection planned at Week 16 or 20 of each cycle: satisfaction with longer interval between 2 injections collected at the corresponding reinjection visit or the last cycle visit
- quality of life changes, measured on the EQ-5D 5L and SF-12 scales: change from baseline to Final Visit.

3.2.3 Safety Endpoint and Evaluation

Safety will be assessed by recording the number, nature and severity of AEs from the time that the subject gives informed consent to the end of study or subject withdrawal. Other safety data will include vital signs.

3.2.4 Exploratory Endpoint and Evaluation

The correlation between full composite AROM and active function (MFS in UL and WS in LL) will be explored.

3.3 Randomisation and Blinding

This is a nonrandomised, open-label, single-arm study.

Recruitment will be stratified by country to ensure that 50% of subjects have the UL as primary TT and 50% of subjects have the LL as primary TT (with $\pm 10\%$ flexibility). This will be controlled at the country level.

3.4 Study Treatments and Dosage

A total dose of AbobotulinumtoxinA 1500 U will be used in each of two injection (treatment) cycles. In each subject, the dose of 1500 U will be split between the UL and LL, as determined by the investigator, based on which limb was considered the primary TT limb at the Baseline Visit and in accordance with prespecified limits. The primary TT will remain the same for both AbobotulinumtoxinA injections and the study duration.

A more detailed description of administration procedures is given in Section 6.1.1.

All subjects will also perform daily GSC therapy. A detailed description of GSC therapy is given in Section 6.1.2.

The investigational medicinal product (IMP) will be packaged by Dreux, France, and delivered to the investigational sites in Europe, or to interim storage in the USA (before delivery to study sites in the USA) and in other countries where interim storage will be needed. A sufficient quantity of IMP will be supplied as well as an acknowledgement of receipt form.

The sponsor's representative will receive a Certificate of Analysis for the batch of IMP that has been used under their study, Material Data Safety Sheet for the active IMP, and Packaging Order which reflects the product release statement.

PROTOCOL FINAL (INCLUDING AMENDMENT #2): 24 JANUARY 2018

The core label texts for all packaging units will be translated or adjusted, to be in compliance with applicable regulatory requirements, national laws in force and in accordance with the local languages. A description of the core text of the IMP labels is displayed below:

- sponsor name
- study number
- pharmaceutical dosage form
- route of administration
- quantity of dose units
- batch number
- specific blank space to enter the subject identification
- "Keep out of reach of children"
- "For clinical study use only" (for nonUS sites)
- "Caution: new drug limited by Federal Law to investigational use" (for US sites)
- name, address and telephone number of the sponsor, contract research organisation (CRO) or investigator (the main contact for information on the product, clinical study and emergency unblinding) (for sites in the European Union)
- storage conditions
- expiry date.

The investigator, or designee, will only dispense IMPs to subjects included in this study. Each subject will only be given the IMP carrying his/her number. The dispensing for each subject will be documented in the electronic case report form (eCRF).

3.5 Study Duration

This study will consist of two open-label injection (treatment) cycles. Each cycle will include postinjection FU visits of up to 20 weeks (see Section 3.1). Subjects are expected to participate in this study for a minimum of 24 weeks (if they have postinjection FU visits up to Week 12 only, following both injections) and a maximum of 40 weeks (if they have postinjection FU visits up to Week 20, following both injections).

The subject's participation in the study will be considered to have ended at the time of the Final Visit. This will be no later than 20 weeks after the second AbobotulinumtoxinA injection.

The overall duration of the study will be between approximately 15 and 18 months. The study will be considered to have started when the first subject provides signed informed consent.

The study will be considered to have ended after the last subject has completed his/her Final Visit.

3.6 Stopping Rules and Discontinuation Criteria

In the following circumstances, subjects will be withdrawn from the study early:

- subject consent withdrawal
- subject lost to follow up
- occurrence of an AE that, in the opinion of the investigator, makes the administration of the study treatment undesirable
- investigator's and/or sponsor's decision to withdraw the subject if it is considered to be in the best interest of the subject
- occurrence of a new ABI

PROTOCOL FINAL (INCLUDING AMENDMENT #2): 24 JANUARY 2018

PAGE 33/105

- continuous failure to comply with the provisions of the study protocol, which is likely to have an adverse impact on the safety or well-being of the subject, or could jeopardise the scientific value of the study
- investigator decides that subject does not need a second AbobotulinumtoxinA administration at Week 20 in Cycle 1.

Subject withdrawal criteria and procedures are described in Section 4.3.

3.7 Investigational Medicinal Product Preparation Storage and Accountability

3.7.1 Investigational Medicinal Product Storage and Security

The investigator, or an approved representative (for example, pharmacist), will ensure that all IMP and any other study related material is stored in a secured area, under recommended temperature (2 to 8°C) monitored storage conditions, in accordance with applicable regulatory requirements.

3.7.2 Investigational Medicinal Product Preparation

The investigator, or an approved representative (for example, pharmacist), will ensure that all IMP is reconstituted and dispensed by qualified staff members.

3.7.3 Investigational Medicinal Product Accountability

All IMP and any other study related material is to be accounted for on the IMP accountability log provided by the sponsor. It is essential that all used and unused supplies are retained for verification (by the sponsor or sponsor's representative). The investigator should ensure adequate records are maintained in the IMP accountability log.

All used or unused clinical study supplies should be destroyed locally and a certificate of destruction should be provided to the sponsor.

3.8 Maintenance of Randomisation and Blinding

Not applicable.

3.9 Source Data Recorded on the Case Report Form

Data will be collected in the eCRF in compliance with FDA 21 CFR Part 11. As required by GCP, the sponsor-assigned monitor will verify, by direct reference to the source documents, that the data required by the protocol are accurately reported on the eCRF.

The source documents must, as a minimum, contain a statement that the subject is included in a clinical study, the date that informed consent was obtained prior to participation in the study, the identity of the study, diagnosis and eligibility criteria, visit dates (with subject status), IMP administration and any AEs and associated concomitant medication.

As required by ICH GCP Section 6.4.9, if some items are recorded directly on the eCRF and are considered as source data, the identification of these data must be documented and agreed between the investigator and the sponsor.

Definition for source data and source documents are given below:

- **Source Data**: All original records and certified copies of original records of clinical findings, observations, or other activities necessary for the reconstruction and evaluation of the study. Source data are contained in source documents (original records or certified copies).
- **Source Documents**: Original documents, data and records (for example, hospital records, clinical and office charts, laboratory notes, memoranda, subjects' diaries or evaluation checklists, pharmacy dispensing records, recorded data from automated

PROTOCOL FINAL (INCLUDING AMENDMENT #2): 24 JANUARY 2018

PAGE 34/105

instruments, copies or transcriptions certified after verification as being accurate copies, microfiches, photographic negatives, microfilm or magnetic media, x rays, subject files and records kept at the pharmacy, at the laboratories and at medicotechnical departments involved in the clinical study).

The subject must have consented to their medical records being viewed by the sponsor's authorised personnel and by local and possibly foreign, competent authorities (CAs). This information is included in the informed consent.

PROTOCOL FINAL (INCLUDING AMENDMENT #2): 24 JANUARY 2018

4 SELECTION AND WITHDRAWAL OF SUBJECTS

4.1 Inclusion Criteria

All subjects must fulfil all of following criteria to be included in the study:

- (1) Subjects aged at least the national legal adult age.
- (2) Subjects with hemiparesis due to ABI (i.e. stroke or Traumatic Brain Injury (TBI)) presenting with muscle overactivity impeding motor function based on investigator's judgement including, but not limited to, at least one of the following requiring BoNT treatment: typical clenched fist; flexed wrist; flexed elbow; or plantar flexed foot.
- (3) At least 12 months since the ABI.
- (4) Naïve or non-naïve to BoNT treatment; if non-naïve, at least 4 months after the last BoNT injection, of any serotype.
- (5) Upper limb active function with an overall score between 2 and 7, as assessed by MFS locally rated score, if the primary TT limb is the UL.
- (6) A 10-metre maximal WS barefoot between 0.2 and 1.4 m/s, if the primary TT limb is the LL. Maximal WS barefoot will be performed preferably without walking aids. However, a cane may be permitted if absolutely necessary (although this may prevent detection of treatment-induced improvements). In this case, the same aid will have to be used for all WS assessments during the study.
- (7) Subjects must provide written informed consent to participate in the study prior to any study-related procedures.
- (8) Female subjects of childbearing potential (not surgically sterile or 2 years postmenopausal) must use a medically accepted method of contraception and must agree to continue use of this method for the duration of the study until the last visit of the subjects and for at least 12 weeks post injection. Acceptable methods of contraception include total abstinence, male partner has had a vasectomy, double barrier method (e.g. male condom plus spermicide, or female diaphragm plus spermicide), intrauterine device, or hormonal contraceptive (oral, transdermal, implanted and injected)..
- (9) Subjects must be willing and able to comply with study restrictions and to remain at the clinic for the required duration during the study period and willing to return to the clinic for the follow-up evaluation as specified in the protocol.

4.2 Exclusion Criteria

Subjects will not be included in the study if any of the following exclusion criteria are met:

- (1) Inability to understand protocol procedures and requirements, which, in the opinion of the investigator, could negatively impact on protocol compliance, in particularly inability to exercise according to the GSC.
- (2) Previous surgery on the affected muscles and ligaments, tendons, nerve trunks, or bones of the treated upper or lower limb.
- (3) Previous treatment with phenol and/or alcohol in any of the treated limbs any time before the study.
- (4) Any medical condition (including severe dysphagia or breathing difficulties) that may increase, in the opinion of the investigator, the likelihood of AEs related to BoNT-A treatment.

PROTOCOL FINAL (INCLUDING AMENDMENT #2): 24 JANUARY 2018 PAGE 36/105

- (5) Subjects treated, or likely to be treated, with intrathecal baclofen during the course of the study or during the 4 weeks before study entry.
- (6) Current, planned or received within the last 4 weeks prior to study treatment, treatment with any drug that interferes either directly or indirectly with neuromuscular function (for example, aminoglycosides).
- (7) Major neurological impairment other than spastic paresis (including major proprioceptive ataxia or apraxia on the paretic side) that could negatively impact on the functional performance of the subject.
- (8) Known disease of the neuromuscular junction (such as Lambert-Eaton myasthenic syndrome or myasthenia gravis).
- (9) Known sensitivity to BoNT-A or any excipient of Dysport.
- (10) Infection at the injection site(s).
- (11) Current pregnancy or lactation. A pregnancy test will be performed at the start of the study for all female subjects of childbearing potential (i.e. not surgically sterile or 2 years postmenopausal).
- (12) Mental condition rendering the subject unable to understand the nature, scope and possible consequences of the study and/or evidence of an uncooperative attitude.
- (13) Abnormal baseline findings or any other medical condition(s) that, in the opinion of the investigator, might jeopardise the subject's safety.
- (14) Subjects who have participated in any therapeutic clinical study/received any investigational agent within 30 days of enrolment.

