- e For all subjects attending the Week 20 visit (Cycle 2), this will be the Final Visit.
- f Informed consent must be obtained before the subject undergoes any study-specific procedures.
- g Demographics: sex and date of birth; race and ethnicity will also be collected if permitted according to local regulations.
- h Disease history: date and type of ABI, date of spasticity development.

PAGE 39/105

PROTOCOL FINAL (INCLUDING AMENDMENT #2): 24 JANUARY 2018

F-FR-52120-228

- i Record all details of previous GSC or physiotherapy within 4 months before Baseline..
- j Record if subject is naïve or non-naïve to BoNT treatment; if non-naïve to BoNT treatment, record dates of the first injection and last injection, which limbs were injected, and BoNT brand and dose used in the last injection.
- k Medical history: any significant past or ongoing medical or surgical conditions (not related to UL or LL spasticity).
- Prior and concomitant medications for UL or LL spasticity: therapies taken from 4 weeks prior to baseline through the study (including the subject's last study visit).
- m Prior and concomitant medications and nondrug therapies: therapies taken from 4 weeks prior to baseline through the study (including the subject's last study visit).
- n Urine pregnancy test: recorded for females of childbearing potential only.
- o Measured at Baseline Visit, second injection visit and Final Visit, only (or early withdrawal). Vital signs: diastolic and systolic blood pressure and heart rate measured in the supine position after 5 minutes rest. Weight will be measured at baseline, second injection and last visit; height will be measured at baseline only.
- p To be performed at the Final Visit (which may be Week 12, Week 16 or Week 20 after Injection 2) or early withdrawal.
- q AROM is measured in each muscle group of the UL and LL (irrespective of whether injected or not).
- r WST is to be performed in the same condition as at Baseline Visit, for example, if a cane was used at the Baseline Visit, the same cane should be used for this test at other visits.
- s The number of days when GSC therapy was not performed since the last visit, as recorded in the subject diary, will be counted and recorded in the eCRF.
- t To be performed only at the last postinjection FU visit after Injection 1 (i.e. the visit where second injection is performed, which may be Week 12, Week 16 or Week 20).

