5.2.1.3 Week 12 (+7 days)

The following assessments will be performed:

- AE check
- concomitant medication review
- physical examination
- vital signs (blood pressure and heart rate, weight) (to be measured only if second injection is given at this visit)
- measurement of AROM against 10 prespecified muscle groups of the UL and LL (irrespective of whether injected or not)
- MFS
- WST (in the same condition as at Baseline Visit, for example, if a cane was used at Baseline Visit, the same cane should be used for this test also)
- subject assessment of satisfaction with GSC

PROTOCOL FINAL (INCLUDING AMENDMENT #2): 24 JANUARY 2018

- subject and physiotherapist completion of Likert scale to assess beliefs that GSC will help to improve functional capacity
- subject GSC diary check and record the number of days GSC not performed in eCRF
- global assessment of benefits by investigator (only if the second injection of AbobotulinumtoxinA is given at this visit)
- global assessment of benefits by subject (or caregiver) (only if the second injection of AbobotulinumtoxinA is given at this visit)
- GSC exercises may be adjusted, based on the clinical judgement of the investigator or physiotherapist.

The investigator will decide if the subject is still responding to treatment or if a second AbobotulinumtoxinA injection is needed at this visit, based on his/her clinical judgement. If a second injection is not given, the subject will return at Week 16. If a second injection is given, this marks the start of Cycle 2 (see Section 5.2.2) and the following procedures will be performed:

- selection of dose split in the UL and LL by the investigator, according to his/her clinical judgement, based on which limb was considered the primary TT limb at the Baseline Visit and prespecified limits (see Section 6.1.1)
- AbobotulinumtoxinA (Dysport) (total dose 1500 U) will be administered by i.m. injection in the subject's UL and LL, according to the agreed dose split.
- 5.2.1.4 Week 16 (± 7 days) (Only if AbobotulinumtoxinA Not Administered at Week 12 Postinjection FU Visit After Injection 1)

This visit is performed only if the second injection of AbobotulinumtoxinA was not given at the previous visit.

If this visit is performed, the following assessments will be performed:

- AE check
- concomitant medication review
- physical examination
- vital signs (blood pressure and heart rate, weight) (to be measured only if second injection is given at this visit)

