8.1.5 Pregnancy

Pregnancy itself is not regarded as an AE unless there is a suspicion that the IMP has interfered with a contraceptive method. If pregnancy occurs during the study, the outcome of the pregnancy will then need to be collected poststudy and it may be necessary to discontinue administration of the IMP.

Information regarding pregnancies must be collected on the AE page of the eCRF and reported to the sponsor within 24 hours. The sponsor will request further information from the investigator as to the course and outcome of the pregnancy using the Standard Pregnancy Outcome Report Form.

The investigator must instruct all female subjects to inform them immediately should they become pregnant during the study. The investigator should counsel the subject, discuss the risks of continuing with the pregnancy and the possible effects on the foetus. Monitoring of the subject should continue until conclusion of the pregnancy, which may involve follow up after the subject's involvement in the study has ended.

Pregnancies with a conception date within 180 days after subject's last dose of IMP must be reported to the investigator for onward reporting to the sponsor.

8.1.6 **Deaths**

All AEs resulting in death during the study period must be reported as an SAE within 24 hours of the investigator's knowledge of the event.

The convention for recording death is as follows:

- AE term: lead cause of death (e.g. multiple organ failure, pneumonia, myocardial infarction)
- outcome: fatal.

The **only exception** is if the cause of death is unknown (i.e. sudden or unexplained death), in which case the AE term may be "death" or "sudden death".

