8.2 Physical Examination

Physical examinations will be performed by a physician at the visits indicated in Table 2.

PROTOCOL FINAL (INCLUDING AMENDMENT #2): 24 JANUARY 2018

Any clinically significant physical examination findings (abnormalities) observed during the study will be reported as AEs.

A urine pregnancy test will be performed at the Baseline Visit for all female subjects of childbearing potential.

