## 1.3.2.3 Other assessments

**Demography and baseline characteristics**: Data collected will include sex and date of birth. Race and ethnicity will also be collected, except for French centers. This will be recorded at baseline visit.

**Disease history**: date and type of ABI, and onset date of spasticity will be recorded at baseline visit.

**Previous BoNT injections**: previous BoNT treatment will be recorded for each subject and for each limb (upper and lower) at baseline visit. If subject is non-naïve to BoNT treatment for a given limb: dates of the first injection and last injection, BoNT brand and total dose used in the last injection will be recorded.

**Previous GSC**: previous GSC followed within the last four months prior to study entry will be recorded at baseline visit.

Selection of primary TT limb (UL or LL): the selection of the TT limb will be recorded at baseline visit according to the clinical judgement of the investigator, in agreement with the subject and in accordance with the dosing rules detailed in the section 1.2.

Urine pregnancy test: this will be recorded at baseline visit for females of childbearing potential only.

CONFIDENTIAL

SAP Version 2.0: 05 October 2018

19/70

**Medical and surgical history**: Complete medical history will include evaluation for any significant past or ongoing medical or surgical conditions not related to UL or LL spasticity. Data will be collected at baseline visit.

**Study drug administration**: Dose administration details will be recorded in the eCRF at each injection. These include the total doses administered (in each limb and for both limbs), the techniques used to target injection with the laterality, and details of the muscles that were injected for each limb and each muscle group (site of administration, number of injection sites and the dose administered by muscle).

**Prior and concomitant medications (excluding UL or LL spasticity)**: General prior medications (excluding UL or LL spasticity) taken from four weeks prior to baseline will be reviewed for each subject at baseline visit. Any general concomitant medications (excluding UL or LL spasticity) will be recorded in the eCRF at each visit.

**Concomitant medications for UL or LL spasticity**: Any concomitant medication for UL or LL spasticity will be recorded in the eCRF at each visit.

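### No pregnancy test is scheduled before the second 1500 U injection, although pregnancy is tested for and excluded before the first

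*Protocol*

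**What the plan says.** Before the first injection:

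- Current pregnancy is exclusion criterion 11 in Protocol 4.2, which continues: "A pregnancy test will be performed at the start of the study for all female subjects of childbearing potential".
- Protocol 8.2 gives the visit: "A urine pregnancy test will be performed at the Baseline Visit for all female subjects of childbearing potential".
- Table 2 in Protocol 5.1 has a single mark for the test, at Visit 1. Its footnote n reads "Urine pregnancy test: recorded for females of childbearing potential only".
- Protocol 5.2.1.1 lists the test among the assessments made before the injection.
- SAP 1.3.2.3 agrees: "Urine pregnancy test: this will be recorded at baseline visit for females of childbearing potential only".

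Before the second injection:

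- Protocol 6.1.1 gives the same total dose, 1500 U, at Week 12, 16 or 20. Only the split between limbs and muscles may change.
- Protocol 5.2.1.3 says "If a second injection is given, this marks the start of Cycle 2 (see Section 5.2.2) and the following procedures will be performed". For Week 12 the list that follows has the dose split and the injection. Weeks 16 and 20 (5.2.1.4 and 5.2.1.5) add a satisfaction question. None of the three visit sections includes a pregnancy test.
- Pregnancy is not among the withdrawal reasons in Protocol 3.6 or SAP 1.3.2.4.
- If pregnancy occurs during the study, Protocol 8.1.5 says "it may be necessary to discontinue administration of the IMP".

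**The concern.** The plan treats pregnancy as a bar to the first dose and checks for it objectively. Before the second dose it does neither. No two passages conflict here, but the protection is uneven between two injections of the same total size.

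Protocol 1.4 says that human data in pregnancy are limited and that use requires the benefit to justify the risk to the foetus. An investigator cannot weigh that for a pregnancy nobody has recognised. A site that follows the plan exactly could therefore give a second 1500 U to a woman who would have been excluded at entry with the same test result. What is at stake is foetal exposure, not the efficacy results.

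**Working it through.** The plan states no figure on this point. The check is a comparison of passages, followed by two short calculations.

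**Step 1. The two dosing occasions side by side**

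| | Injection 1 | Injection 2 |
|---|---|---|
| Total dose | 1500 U | 1500 U |
| Urine pregnancy test before dosing | Yes (4.2, 5.2.1.1, 8.2, Table 2) | None (Table 2, 5.2.1.3 to 5.2.1.5) |
| Rule against dosing in pregnancy | Yes, exclusion 11 | None; 8.1.5 says only that stopping may be necessary |
| Vital signs before dosing | Yes | Yes (Table 2, footnotes a and o) |

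The exclusion criteria govern entry to the study, and Table 2 marks the eligibility check at Visit 1 only. Exclusion 11 is therefore not re-applied at reinjection.

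**Step 2. Would another control find an unrecognised pregnancy?**

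- Contraception (4.1, criterion 8): the subject "must agree to continue use of this method for the duration of the study until the last visit of the subjects". This lowers the chance of pregnancy but does not detect one. The plan required it at entry and still tested before dose 1.
- Self-report (8.1.5): "The investigator must instruct all female subjects to inform them immediately should they become pregnant during the study". This works only once she knows.
- A general health question at each visit and call (8.1.3): the same limit.
- Physical examination at each visit (Table 2): no passage gives it the purpose of detecting pregnancy.
- Best-interest or discretionary withdrawal (3.6, 4.3): this needs the pregnancy to be known. Pregnancy is normally not an adverse event under 8.1.5, so the adverse-event withdrawal reason does not apply automatically.

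**Step 3. Time from the only test to the second dose**

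The visit windows are those in Table 2.

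- Earliest: Week 12, whose window is +7 days only: 12 × 7 = 84 days.
- Latest: Week 20 plus 7 days: 20 × 7 + 7 = 147 days.

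**Step 4. Expected number of unrecognised pregnancies at injection 2**

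Formula: women of childbearing potential × yearly pregnancy rate on contraception × weeks unrecognised / 52.

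- From the documents: about 155 subjects planned (3.1).
- Assumed: 10% to 20% are women of childbearing potential, giving 155 × 0.10 = 15.5 (16 women) to 155 × 0.20 = 31 women.
- Assumed: 2% to 8% become pregnant per year on contraception.
- Assumed: a pregnancy goes unrecognised for 4 to 6 weeks.

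Low: 16 × 0.02 × 4/52 = 0.025. High: 31 × 0.08 × 6/52 = 0.286.

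Allowing for the planned 5% dropout (10.2) changes little: 0.025 × 0.95 = 0.024 and 0.286 × 0.95 = 0.272.

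**The case against.** The strongest case on the other side accepts that no test is scheduled and disputes its importance.

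- **The hazard is mild in the plan's own account.** Protocol 1.3 reports no teratogenicity in rats or rabbits. Protocol 1.4 reports harm in animals only at doses toxic to the mother. This is a fair qualification and belongs beside the caution in 1.4. It did not stop the plan from excluding and testing for pregnancy at entry, and the same reasoning carries over to dose 2.
- **Known pregnancies are already manageable.** Injection 2 is never automatic, since the investigator decides at each visit, and 3.6, 4.3 and 8.1.5 allow the dose to be withheld. This stands. The practical gap is the unrecognised pregnancy.
- **A fixed ban is stricter than the benefit-risk wording in 1.4.** That is true, but it matches exclusion 11. Leaving the study when injection 2 is not given also matches the existing Week 20 rule in 3.1 and 3.6.
- **The expected number is below one even at the high end.** This stands too. The range also overstates what a strip would catch, because some pregnancies would be too early to detect.
- **The cost includes an amendment.** Protocol 12.1.1 requires ethics approval, and 13.1 discourages amendments once the study has started. SAP 3.2.18 shows that enrolment was complete by version 2.0, so few second injections may have remained by then. This limits the benefit for this trial, not the soundness of the change to the design.

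**Conclusion.** The concern holds. The urine test is scheduled only at baseline, no test precedes the second 1500 U, and no passage forbids that dose in a pregnant subject. This is a small patient-safety gap that is cheap to close. It does not threaten the validity of the trial: no endpoint definition, analysis method or sample size depends on it.

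The absence of the test and the 84 to 147 day interval come directly from the documents. The estimate of 0.02 to 0.29 cases does not: apart from the 155 subjects, every input is assumed, so it should be read only as well under one expected case in the trial. The argument for acting rests on the possible seriousness of foetal exposure and the low burden of the test, not on frequency.

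**What to change.** 1. In Table 2, mark the urine pregnancy test in the second-injection column, before dosing, for women of childbearing potential.
2. Add the same line to Protocol 5.2.1.3, 5.2.1.4 and 5.2.1.5, to apply only when the second injection is to be given at that visit. Bring Protocol 8.2, SAP 1.3.2.3 and the SAP schedule table into line.
3. In Protocol 3.6 and 8.1.5, state that a positive test means injection 2 is not given, that the subject attends the Early Withdrawal Visit, and that the pregnancy is followed as 8.1.5 already requires.

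The cost is one strip per woman concerned: about 16 to 31 if 10% to 20% of subjects are of childbearing potential (an assumption), and no more than about 155 in any case. No extra visit is needed. The change does need a protocol amendment with ethics approval, and an update to the case report form if the result is to be recorded. The downside is that, rarely, a subject will miss injection 2 and so drop out of the mITT population. She would remain in the ITT analysis, provided she meets its other conditions, with her last postbaseline responder status, or as a nonresponder if she has none.
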